# 1.2 Objectives

The main objective of this multi-center collaborative study is to evaluate sequencing (both whole exome sequencing [WES] and WGS) as a prenatal diagnostic tool in pregnancies with a structural anomaly and a negative or only non-causal karyotype/ chromosome microarray analysis (CMA). Specifically, the aims are as follows:

- 1. To determine in pregnancies with structural anomalies which are CMA negative (or have only non-causal findings), the frequency of pathogenic, likely pathogenic, and uncertain genomic variants identifiable by sequencing.
  - a. Examine the relative yield of pathogenic, likely pathogenic, and uncertain genomic variants identifiable by WGS compared with analysis of the coding sequence alone (simulating WES).
- 2. To evaluate the impact of having sequencing results available prenatally on clinical management, including health care utilization and costs, comparing outcomes of pregnancies and neonates with *in utero* diagnosed structural anomalies that have undergone prenatal sequencing with those that have not.
- 3. To evaluate the educational/counseling and psychosocial needs of pregnant couples having a fetus with a structural anomaly and assessing the psychological impact of sequencing and return of results

- on couples and determine the correlation with demographic factors, knowledge and attitudes about genetics, baseline parental attitudes and beliefs, and genetic test results.
- 4. To expand the diagnostic yield and clinical utility of fetal sequencing by developing and optimizing bioinformatic tools capable of efficiently and rapidly identifying pathogenic and likely pathogenic variants with prenatal presentations.

# 1.3 Purpose of the Study Protocol

This protocol describes the background, design and organization of the study and may be viewed as a written agreement among the study investigators. It is approved by the funding agency (NICHD), the study Steering Committee, the Data Safety Monitoring Board (DSMB), the single Institutional Review Board (IRB) of the Clinical Coordinating Center and participating laboratories before recruitment begins. Any changes to the protocol during the study period require the approval of the Steering Committee and the IRB.

A manual of operations supplements the protocol with detailed specifications of the study procedures.

# 2 Background

#### 2.1 Introduction

With advances in prenatal imaging, increasingly there is the ability to detect birth defects prenatally and use this information to optimize perinatal and neonatal management. Simultaneously, molecular genetic diagnostics have facilitated more precise identification of the underlying cause of these birth defects and provided additional prognostic information to improve prenatal and postnatal management. The first major improvement in prenatal genomic diagnosis was chromosome microarray analysis (CMA) which identifies copy number variants (CNVs) of 100 kb to 10Mb that are below the resolution of most karyotypes. A multicenter study evaluating the clinical utility of prenatal CMA reported that CMA identified the same aneuploidies and unbalanced rearrangements as karyotyping but also identified additional, clinically significant cytogenetic information. Among women with a normal karyotype, CMA identified clinically relevant deletions or duplications in 6.0% with a fetal structural anomaly and in 1.7% of those with indications of advanced maternal age or positive aneuploidy screening results. The frequency of CNVs varied by anomaly, with the highest frequency (16%) occurring in fetuses with cardiac defects.

Congenital anomalies affect 2-4% of all infants and are responsible for 20% of perinatal deaths. Prenatal genetic evaluation of fetal anomalies is limited to karyotype and CMA performed on amniocytes or chorionic villi. The karyotype is abnormal in 20-25% and CMA is abnormal in 5-10% of fetal anomalies, leaving 60-70% without a genetic diagnosis. WGS is the process of determining the complete DNA sequence of an organism's genome at a single time and includes both the coding and non-coding regions. Whole exome sequencing (WES) analyzes only the coding regions of the genome (exons; DNA code for making proteins). Until recently, researchers have elected to use WES because it costs less and because the functional consequences of positive findings occurring within coding regions of genes are much easier to interpret. Because of its high cost and incomplete knowledge about the role of non-coding variants in disease, WGS has primarily been used as a research tool. This may change as sequencing costs decrease and knowledge of the functional consequences of non-coding genetic variants increases. Numerous recent reports describe the speed and reliability of WGS in the context of rapid clinical sequencing since library preparation is not required making WGS an advantageous technology for rapid genomic testing in the future.

Prenatal sequencing has the potential to alter the life course and reduce morbidity and mortality by guiding pregnancy management, delivery plans and/or the treatment of fetuses and newborns with some genetic abnormalities. One example is *in utero* fetal intervention now performed for certain anomalies including aortic stenosis to avoid hypoplastic left heart syndrome, urinary diversion for posterior urethral valves, drainage of pleural effusions and chylothorax, surgical repair for spina bifida, tracheal occlusion for congenital diaphragmatic hernia, and amnio-infusion for renal agenesis. For all of these, knowing their genetic etiology aids clinical management decisions by providing information about other associated medical features that affect the likelihood of success of the intervention. In addition, prenatal diagnosis of some metabolic conditions could guide early postnatal treatment and avoid metabolic crises that can lead to long term neurocognitive deficits. For example, pyruvate dehydrogenase deficiency can present prenatally with structural anomalies and is modifiable by a ketogenic diet and thiamine supplementation. Finally, mesenchymal stem cell transplantation for osteogenesis imperfecta has been reported to increase skeletal mineralization and growth velocity without adverse outcomes. With developments in gene and stem cell therapy, this type of treatment may increasingly become an option for other conditions.

# 2.2 Preliminary Studies

#### 2.2.1 Postnatal Studies

WES, which analyzes the coding regions of the genome (exons) is a powerful diagnostic tool in adults and children with genetically heterogeneous conditions.  Compared with a 10% diagnostic yield with karyotype and CMA, postnatal WES has diagnostic yields of >30% in adults and children with phenotypes suggestive of monogenic disorders.  The mean and median overall diagnostic yields of a series of 16 studies was 36% and 38%, respectively, but was highly dependent on the *a priori* risk for a monogenic disorder. In addition to the diagnostic utility of WES in these populations, WES analysis has resulted in discovery of new disease genes with pleiotropic phenotypes.

WGS is now gaining traction as a diagnostic and discovery strategy for adults and children with a suspected genetic disorder that remains undiagnosed after WES analysis, or as a first-line approach in lieu of WES. WES includes an exon capture step, which adds time and reagent costs, and biases against coverage in GC-rich regions. WGS does not include this selection step, providing more uniform coverage which allows a lower mean read depth, offers ability to detect copy number variants (CNVs) with higher resolution than CMA and more complex balanced re-arrangements. The lower read depth however will also make it more difficult to detect mosaic mutations which are an important source of mutations in neurodevelopmental disorders including autism and epilepsy. WGS was found to detect up to 3% of protein-coding variants missed by WES. Recent WGS studies have found more causative variants in coding and non-coding regions in autism. In addition, an increased burden of rare *de novo* variants in non-coding regions for congenital heart disease and diaphragmatic hernia has been seen ([name]; unpublished data).

#### 2.2.2 Prenatal Studies

Only a few case series of prenatal WES have been published to date with a wide range of indications, including pregnancy terminations, fetal demises with fetal anomalies, euploid fetuses with sonographically detected single or multiple fetal structural anomalies, and increased nuchal translucency (NT) > 3.5 mm have been reported with widely variable diagnostic yields of 6.2 - 80%. The 2 largest series of trio exomes on over 200 fetal anomalies each had overall diagnostic rates of 6.2 and 7.5%, but was higher (14.3% and 16.0%) for fetuses with multiple anomalies.

Table 1. This table describes the frequency of pathogenic variants by whole exome sequencing in various publications

First Author, Year	# Cases	Cohort Criteria	Method	Pathogenic Variants*
Normand, 2018 	146	Fetuses with ultrasound anomalies and a suspected Mendelian disorder	62 Trio	46/146 (32%)
Aarabi, 2018 	20	1 or more major structural congenital anomaly detected by ultrasound	Trio	4/20 (20%)
Fu, 2017 	196	Fetuses with structural abnormalities	147 Proband- only	34/147 (23.1%) 13/49 (26.5%)
			49 Trio	,
Lei, 2017 	30	Fetuses with congenital anomalies of the kidney and urinary tract	23 Proband-only	3/23 (13%)
			7 Trio	1/7 (14%)

			Total	4/30 (13.3%)
Vora, 2017 	15	Fetuses with multiple congenital anomalies highly suggestive of an underlying genetic disorder	Trio	7/15 (47%)
Yates, 2017 	84	Fetuses with ultrasound abnormalities that resulted in fetal demise or pregnancy termination	29 Proband-only	4/29 (14%)
			45 Trios	11/45 (24%)
			6 Quads/4 Maternal Duos	2/10 (20%)
			Total:	17/84 (20%)
Pangalos, 2016 	14	Prenatal ultrasound abnormalities or malformations	Proband-only	6/14 (43%)
Alamillo, 2015 	7	Multiple congenital anomalies on prenatal ultrasound	Trio	4/7 (57%)
Drury, 2015 	24	Fetuses with an increased NT (>3.5 mm) or other ultrasound abnormality	14 Proband-only	2/14 (14%)
		unusound donormanty	10 Trio	3/10 (30%)
			Total	5/24 (21%)
Carss, 2014 	30	Structural abnormalities identified on prenatal ultrasound	Trio	3/30 (10%)
Yang, 2014 	11	Terminated fetuses with anomalies	Trio	6/11 (54%)

#### 2.2.3 Healthcare Utilization and Cost

Integration of WES or WGS into clinical care requires not only demonstration of the ability to identify the underlying etiology of a disorder but also requires evidence that care is improved, providing value to the health care system. While WGS is currently a relatively expensive test (≥\$15,000 per trio), the information may lead to significant alterations in care utilization. Given that healthcare costs can be \$250,000 or more in the first year of life for some complex congenital anomalies, the genetic diagnostic information may be net cost saving. Even if not cost-saving, if clinical outcomes are improved significantly, the incremental cost of WGS may be justifiable based on its cost effectiveness. Recent studies in critically ill neonates and infants have suggested that establishing a diagnosis leads to more focused management and reduction in healthcare utilization and reduced cost. Meng et al evaluated diagnostic WES for 278 critically ill infants within the first 100 days of life and found a genetic diagnosis in 36.7%. These new diagnoses led to care modification in 52%, including initiation of new subspecialist care, redirection of care, changes in medication/diet, or completion of major procedures (e.g., transplant). The greatest impact was in infants receiving rapid "critical trio sequencing". A metaanalysis found that change in clinical management by WGS results was 27% (4 studies with 136 children) compared with 17% by WES (12 studies and 992 children) and 6% by CMA (8 studies of 4,271 children). 40 Another study evaluating the cost-effectiveness of WES in a pediatric setting reported the mean duration of the diagnostic odyssey was 6 years, and that the diagnostic trajectory for WES performed at the initial tertiary presentation resulted in an incremental saving of \$6800 per additional diagnosis compared with the standard diagnostic pathway. In summary, studies have suggested that sequencing early in the disease course may provide the maximal benefit by modifying clinical management, reducing the time to diagnosis and cost.

# 2.2.4 Educational & Psychosocial Needs

The added prognostic information about health, treatability, life expectancy and neurodevelopmental, behavioral and cognitive function is far beyond what is learned from ultrasound findings and standard testing, and can have a powerful impact on parents. Identification of fetal genomic information has significant value to the management of the pregnancy. Ultrasound offers an anatomic phenotype but is incapable of evaluating long-term neurocognitive potential, limiting accurate prognostication and counseling. Karyotyping and CMA can offer disease specific counseling in a combined ~30-40% of detectable cases to provide couples with the information necessary to make informed reproductive decisions, leaving significant ambiguity in 60-70%. Equally important, knowledge of the genotype can direct additional fetal, neonatal and pediatric management.

Efforts to understand the psychosocial and behavioral impact of integrating genomic technologies into adult and pediatric practice are ongoing, but to date, little empirical work has been done to understand the unique challenges of applying genomic sequencing to a prenatal population. Attitudes towards prenatal screening and diagnosis are influenced by ethnicity, socioeconomic status, cultural and religious beliefs, and experiences with disability.

While WGS results may illuminate the situation when a well-known genetic condition is diagnosed, there are challenges in counseling for some of the newer genetic conditions for which less data are available. In CMA, variants of uncertain clinical significance (VUS) and those associated with variable expressivity occur in a proportion of cases with structural anomalies (5.3%) and require extensive genetic counseling. Other counseling issues include the identification of adult onset disorders of both the fetus and parent. To understand attitudes and unmet needs in the adoption of CMA testing semi-structured interviews with parents and counselors were performed to evaluate pre-test counseling, reporting of results, and assessing patient and provider experiences. From the patient perspective, 5 key themes were identified 1) accepting CMA testing was an easy decision to make as patients would obtain additional information on their baby's health at no additional cost, 2) patients were blindsided by the results in cases where they initially received a normal karyotype result followed by an abnormal CMA, 3) abnormal results left patients shocked, anxious, confused and overwhelmed, 4) patients needed support to manage, understand and act on the microarray results, and 5) uncertain findings were felt to be toxic knowledge and patients wished they did not receive the results. It is anticipated that the needs for prenatal sequencing will be similar to those of prenatal CMA and that prior studies will inform the educational and support materials developed for prenatal sequencing.

# 2.3 Rationale for the Study

Sequencing itself is a transformative technology to identify comprehensively genetic variants accounting for a phenotype, but its application to prenatal diagnosis has not been investigated prospectively in a large cohort. This study population of unselected consecutive cases will be unique in that the majority of published series to date have only included select phenotypes felt to have a genetic etiology. It is possible that these studies have overestimated the frequency and underestimated the phenotypic variability of *in utero* genetic disease based upon the case ascertainment. A more comprehensive, less biased evaluation of the molecular etiology of birth defects should lead to the discovery of previously unknown genes and phenotypic associations. To date, only descriptive series of the diagnostic yield of selected prenatal WES or WGS have been reported on fetuses with a structural anomaly, but none have evaluated the benefit of a specific genetic diagnosis. 36,37,51-53

This study will be the first to perform a cost-effectiveness analysis to evaluate whether prenatal knowledge of the genetic cause of a fetal single-gene disorder will lead to altered fetal/neonatal management, costs, and outcomes. Also important are the pertinent psychosocial effects of introducing sequencing into a prenatal setting.

Before integration into standard care, the diagnostic capabilities of prenatal WGS must mature by developing new bioinformatic tools to specifically facilitate accurate and efficient prenatal interpretation and novel gene discovery. This can be accomplished initially by analyzing and reporting the variants from the coding regions of the genome and then subsequently analyzing the non-coding regions, allowing comparison of the differences in diagnostic yield. The current missing pieces are insufficient WGS data in fetuses with abnormalities, the lack of variant analysis algorithms tuned to the prenatal setting, and insufficient publicly deposited data to inform clinical care for prenatal genomic testing and rare developmental disorders. As more data become available (WGS data from adults, more WES/WGS from more diverse communities, Human Cell Atlas data, and ATAC seq data from appropriate times in development), it will increasingly be possible to interpret the coding and noncoding regions that are relevant to developmental disorders.

# 3 Study Design

# 3.1 Design Summary

This multicenter, observational cohort study will evaluate prenatal sequencing among pregnancies with fetal structural anomalies recruited at university based medical centers and evaluated at four genetic laboratories. A total of 1,100 pregnancies with fetal structural anomalies and meeting eligibility criteria will be enrolled into the study. Of these, 750 will undergo prenatal genomic sequencing (prenatal sequencing group) and the remaining 350 pregnancies will not have any prenatal genomic sequencing (unsequenced prenatal group). Enrollment of pregnancies with an isolated nuchal translucency measurements  $\geq$  3.5 mm and < 4.5 mm without evidence of cystic hygroma will be restricted to 5% within each group (sequenced and unsequenced) and isolated estimated fetal weight <5th %ile also will be restricted to 5% for each group (sequenced and unsequenced).

The prenatal sequencing group will be used to determine the frequency of pathogenic, likely pathogenic, and uncertain genomic variants identifiable by sequencing and the relative yield of sequencing. The prenatal sequencing group will be compared with the unsequenced prenatal group (prospective and retrospective) to evaluate health care management, health care utilization and cost, and perinatal outcomes. The prenatal sequencing group will be compared with the prospective unsequenced prenatal group to evaluate psychosocial needs of pregnant couples. Mothers, fathers and infants will be followed through 1 year postpartum for participants enrolled prospectively.

# 3.2 Eligibility Criteria

#### 3.2.1 Prenatal sequencing group

#### 3.2.1.1 Inclusion Criteria

- 1. Fetus identified by ultrasound and/or MRI with at least one of the following:
  - a. One or more suspected major structural anomalies (Appendix A)
  - b. A nuchal translucency measurement of  $\geq$  3.5 mm and < 4.5 mm without evidence of cystic hygroma
  - c. A fetus less than 24 weeks 0 days gestation with normal anatomy and sonographically estimated fetal weight <5th %ile without maternal hypertension, type I diabetes, or other maternal disorders known to alter fetal growth.
- 2. Negative prenatal CMA (or those with CMA findings not related to the ultrasound finding)
- 3. Singleton gestation or dichorionic diamniotic (DCDA) twin gestation.
- 4. Gestational age less than 36 weeks, 0 days to allow for availability of sequencing results before delivery

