#### 3.2.2.2 Exclusion Criteria

- 1. Prenatal or postnatal (prior to neonatal discharge) CMA with pathogenic or likely pathogenic variants that are related to the prenatal ultrasound finding
- 2. Maternal or paternal age less than 18 years old
- 3. Proven infectious, teratogenic, or other genetic cause of fetal anomaly
- 4. Positive prenatal NIPT screening for trisomy 21, 18 or 13. Positive 22q11.2 prenatal NIPT testing with consistent ultrasound findings is also an exclusion.
- 5. For twin gestation, anomalies in both fetuses (NT, IUGR, or structural anomaly)
- 6. Monochorionic diamniotic (MCDA) and monochorionic monoamniotic (MCMA) twins as well as higher-order multifetal gestations.
- 7. Planned termination of the fetus or intrauterine fetal demise (IUFD)
- 8. Unable to consent both genetic parents
- 9. Parental unwillingness to participate in 1 year postnatal follow-up

10. Language barrier (non-English or Spanish speaking)

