#### 4.2 Enrollment

# 4.2.1 Prenatal sequencing group

For the prenatal sequencing group, chorionic villus sampling (CVS) or amniocentesis will be performed per standard of care. For twin gestations, either the twin with the anomaly or both twins will be sampled according to local clinical practice. For CVS sampling, a portion of the villi, cultured villi or extracted DNA will be sent to the sequencing laboratory. For amniocentesis, the usual draw of 40cc of fluid will be divided by the cytogenetics lab, with a portion used for clinical testing (minimum standard amount as per diagnostic laboratory practice) and from the remainder, DNA will be extracted for sequencing in a CLIA laboratory. Additional DNA for sequencing will be extracted from the cultured cells and the sequencing lab will determine which is the optimal source for sequencing, after quality and quantity verification. Amniotic fluid supernatant will be kept for future research.

Potentially eligible participants will sign either the screening consent form or study consent form prior to collection of parental samples. Thirty ml of maternal blood or buccal swab/saliva will be collected for sequencing and future research; future research will include investigating non-invasive prenatal testing (NIPT). Paternal blood (up to 10 ml) or buccal swab/saliva will be collected for sequencing and future research. Every effort will be made to obtain samples from both parents prior to or at the time of the diagnostic procedure. If the father is absent, a sample will be obtained as soon as possible. If no paternal sample is obtained, the participant will be classified as a screen failure and will not be enrolled into the study. The parental samples will be sent for DNA extraction as soon as they become available.

If the clinical karyotype, CMA or any other non-sequencing test result is known to be positive prior to sequencing, and felt to be causative of the anomaly, the karyotype/CMA results will be recorded, the participant will be classified as a screen failure and not enrolled, and parental samples/DNA will be discarded.

If the clinical karyotype/CMA results are negative (or non-causative), eligibility criteria will be confirmed, the participant and genetic father will sign the study consent form (if not already signed),

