#### "Expedited" prenatal sequencing

An alternative to the prenatal diagnostic flow described above permits prenatal sequencing to be performed in parallel with the CMA, i.e. before the fetus is confirmed as CMA negative. This diagnostic workflow is at the discretion of the study research team and participants will be considered enrolled once they have signed the study consent and parental samples have been collected. If the CMA is negative or unrelated to the fetal anomaly, the case will continue to be part of the prenatal sequencing group and included in the analyses. In pregnancies in which the CMA result is found to be pathogenic or likely pathogenic (and presumed causal of the anomaly), sequencing will be discontinued or if already completed the results will be recorded and reported to the family in the appropriate manner. The karyotype/CMA results will be recorded; however, follow-up of the pregnancy through delivery will not take place, these participants will not be included in the analyses and not contribute to the sample size.

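### The protocol gives no single rule for a CMA variant of uncertain significance related to the anomaly, and its eligibility lists treat such a fetus differently in the sequenced and control groups

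*Combined protocol and SAP*

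**What the plan says.** All references are to version 1.8 of the protocol.

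- **Sequenced group, eligibility (3.2.1.1 item 2):** "Negative prenatal CMA (or those with CMA findings not related to the ultrasound finding"). The test is relatedness alone.
- **Sequenced group, standard route (4.2.1):** screen failure applies "If the clinical karyotype, CMA or any other non-sequencing test result is known to be positive prior to sequencing, and felt to be causative". The go-ahead sentence begins "If the clinical karyotype/CMA results are negative (or non-causative), eligibility criteria will be confirmed".
- **Sequenced group, expedited route (4.2.1):** "If the CMA is negative or unrelated to the fetal anomaly, the case will continue to be part of the prenatal sequencing group". Removal is governed by a separate sentence: "In pregnancies in which the CMA result is found to be pathogenic or likely pathogenic (and presumed causal of the anomaly), sequencing will be discontinued".
- **Both control groups, eligibility (3.2.2.2 item 1 and 3.2.3.2 item 1):** exclusion applies to a prenatal or pre-discharge "CMA with pathogenic or likely pathogenic variants that are related to the prenatal ultrasound finding". The test is pathogenicity class and relatedness together.
- **Prospective controls, procedure (4.2.2):** those planning invasive testing enrol once karyotype and CMA are confirmed negative. Those who decline invasive testing enrol at diagnosis. If they later elect it, they are analysed when the result is negative or non-causal. Follow-up stops only for a pathogenic or likely pathogenic causal CMA found before neonatal discharge.
- **Retrospective controls, procedure (4.2.3):** no CMA condition beyond the eligibility list.
- **Yield population (5.1):** participants whose karyotype and CMA are normal. The objectives in 1.2 instead say negative or non-causal.
- **Between-group analysis (5.3):** only pathogenic or likely pathogenic causal findings before neonatal discharge lead to exclusion, in either group.

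**The concern.** The sequenced and unsequenced groups are compared directly on hospital charges (the second primary outcome) and on perinatal outcomes, and they are not randomised. Any rule that admits a type of fetus to one group more readily than to the other adds a case-mix difference that the design could have avoided. A fetus with a related but unproven copy-number finding is such a type. On the eligibility lists it is barred from the sequenced group and admitted to both control groups.

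The point also touches the first primary outcome. Whether a related VUS belongs in the denominator of the sequencing yield depends on which of three descriptions is followed: normal CMA (5.1), negative or non-causal CMA (1.2), or negative or unrelated CMA (3.2.1.1). Two sites applying the text in good faith could count the same fetus differently.

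**Working it through.** **Step 1. Follow one fetus through each rule.** Take a fetus with a CMA VUS that the site judges related to the anomaly, with causality unproven.

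| Rule | Outcome for this fetus |
|---|---|
| 3.2.1.1 item 2, sequenced | Fails: not negative, and the finding is related |
| 4.2.1 standard, screen failure | Not clearly caught: requires positive and felt to be causative |
| 4.2.1 standard, go-ahead | May count as non-causative, but eligibility is then confirmed, which returns to 3.2.1.1 |
| 4.2.1 expedited, stays | No: neither negative nor unrelated |
| 4.2.1 expedited, removed | No: neither pathogenic nor likely pathogenic |
| 3.2.2.2 item 1, prospective control | Passes |
| 3.2.3.2 item 1, retrospective control | Passes |
| 4.2.2, control planning invasive testing | Fails as worded: result is not confirmed negative |
| 4.2.2, control electing invasive testing later | Undefined: depends on whether VUS means non-causal |
| 4.2.2, control first tested after birth | Stays: follow-up ends only for a pathogenic or likely pathogenic causal result |
| 4.2.3, retrospective control | Passes: no further CMA rule |
| 5.1, yield population | Outside, if normal is read literally |
| 5.3, analysis exclusion | Not removed, in either group |

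The lists in 3.2 therefore conflict, and the procedural text does not repair them. The control routes that are clearly open are retrospective enrolment and first testing after birth.

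**Step 2. Upper bound on the number affected.** The only frequency in the documents is the 5.3% in section 2.2.4. It pools CMA VUS with variable-expressivity findings and is not limited to findings related to the anomaly, so it is an upper share. Section 5.1 assumes 500 sequenced and 300 control participants in the charge analysis.

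- Analysed controls: 0.053 × 300 = 15.9, about 16.
- Enrolled controls: 0.053 × 350 = 18.6, about 19.
- Sequenced group, yield: 0.053 × 750 = 39.8, about 40. Sequenced group, charges: 0.053 × 500 = 26.5.
- With an assumed share of 1%, analysed controls affected: 0.01 × 300 = 3.

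**Step 3. Possible shift in the charge comparison.** Suppose sequencing has no effect, a share *p* of controls are related-VUS fetuses, the sequenced group has none, and these fetuses cost *r* times the others. The expected ratio of arithmetic means (sequenced to control) is 1 / (1 + p(r − 1)). The documents give no *r*, so 0.75 to 2.0 is assumed.

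- p = 0.053, r = 2.0: 1 / 1.053 = 0.950.
- p = 0.053, r = 0.75: 1 / 0.98675 = 1.013.
- p = 0.01, r = 2.0: 1 / 1.01 = 0.990.

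The plan's target ratio is 0.80.

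**Step 4. Power cost of the exclusion analysis.** From the stated mean of $277,902 and SD of $389,484, CV = 1.4015 and log-scale SD = √ln(1 + 1.4015²) = 1.0424. The effect is |ln 0.80| = 0.2231.

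- 500 v 300: SE = 1.0424 × √(1/500 + 1/300) = 0.0761; power = Φ(0.2231/0.0761 − 1.96) = 83.4%. The plan states 80%. If the dollar SD is held equal in both groups the result is 79.5%, so the stated figure is not disputed here.
- 500 v 284.1 (controls reduced by 5.3%): 82.2%.
- 473.5 v 284.1 (both groups reduced by 5.3%): SE = 0.0782; power = Φ(2.852 − 1.96) = 81.4%.

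**The case against.** A reader might infer from the eligibility lists that these fetuses enter only the control side. The documents do not support that. Section 4.2.2 requires a confirmed negative CMA for prospective controls planning invasive testing, which is stricter than the sequenced criterion. On the sequenced side, the standard route screen-fails only results that are positive and felt to be causative, and an unproven VUS may be read as non-causative. If a site enrols it, section 5.3 leaves it in. The eligibility check within the go-ahead sentence weakens that second argument, because it sends the case back to 3.2.1.1, but it does not remove the ambiguity.

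A reader might also infer that different thresholds were chosen deliberately. The amendment history points the other way. Its 13 November 2020 entry applies the pathogenic-or-likely-pathogenic-and-causal threshold to 4.2.1 and 4.2.2 together, which suggests incomplete alignment of wording.

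Nor is it an error in itself to leave a related VUS out of the yield, since section 5.1 speaks of a normal CMA. That objection stands. What remains is that 1.2, 3.2.1.1 and 5.1 describe that population in three ways.

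Finally, the size is limited. The 5.3% overstates related VUS, and controls may have no CMA at all, so the count of 16 is a ceiling.

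**Conclusion.** The inconsistency is real and lies within the current text. The eligibility lists conflict, the two expedited sentences leave a related VUS unassigned, and 4.2.1, 4.2.2, 5.1 and 5.3 do not resolve it. The supportable conclusion is that such fetuses *can* be admitted as controls by two open routes while being screened out of sequencing. One-sided entry as a rule is not shown.

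The effect is probably small. Even if the asymmetry operated fully at the 5.3% ceiling, and with an assumed cost multiple of 0.75 to 2.0, the charge ratio under no true effect would lie between about 0.95 and 1.01. This is a minor point, worth correcting because the correction is cheap. The share of controls that is retrospective or tested only after birth is not given, so the actual number cannot be fixed more closely.

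**What to change.** Reconcile 3.2.1.1 item 2, 4.2.1 (standard and expedited), 3.2.2.2, 3.2.3.2, 4.2.2, 5.1 and 5.3 to one CMA threshold, worded identically for all groups. The threshold already in 5.3 (pathogenic or likely pathogenic, and causal) is one candidate. Whichever is chosen, 4.2.2 and the population wording in 5.1 must change with it. Otherwise invasively tested controls would still need a negative CMA while sequenced cases would not, and the asymmetry would run the other way.

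For participants already enrolled, flag every related CMA VUS from the reports that sections 4.3 and 4.6 send to the DCC. Repeat the charge and perinatal comparisons once, excluding flagged cases from both groups. State alongside that CMA status is unknown in untested controls, so this analysis cannot fully equalise case mix.

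The cost is a wording amendment, one derived flag and one additional analysis, with power for that analysis no lower than about 81% on the working above. Under the 5.3 threshold, a few sequenced cases would carry an unresolved copy-number finding. These should be reported separately in the yield.
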